Indications for ORIF include bilateral fractures(relative), severe dislocation (> 10 degrees), other facial fractures affecting the occlusion, foreign bodies, lateral displacement of the condyle, and condyle displacement into the middle cranial fossa(11), mandibular nerve paraesthesia(12). Condylar fractures can be reached through trans -facial or intraoral approaches (13,14) .Singh et al (15) published the largest blinded, randomized controlled trial comparing open techniques with closed management; they concluded that both treatment options carry promising outcomes. However, the surgically treated group showed better results in all objective and subjective functional outcomes except for occlusion.

The gold standard osteosynthesis system is the use of two miniplates fixation secured with four screws each (16). However, some drawbacks such as; difficult accessibility that elongates operation time especially in higher fractures the use of double miniplates is associated with risk of facial nerve injury and subsequent facial nerve palsy. Moreover, the little amount of bone that is always encountered at the proximal part of the fracture (17).

Recently, Osteosynthesis devices with various shapes and sizes as single L, Y plate, or 3-D plate are used for the management of condylar fractures. Manufacturers tend to develop such systems to gain outcomes similar to that of the conventional 2 mini-plate system regarding functional stability and rigidity with less cost, less complications and less effort(17).

Several studies were conducted on three-dimensional plating systems such as Rhomboid, Trapezoid and Delta shaped plates that yielded good outcomes (17–21). One study claimed that trapezoidal condylar plate is convenient for low sub condylar fractures because of its wide dimensions, On the other hand, delta plate is suitable for both high and low sub condylar fracture. ((22–24)

The aim of this study is to evaluate the versatility of three-dimensional delta plate in reduction and fixation of this type of fracture in adult patients presented with unilateral sub-condylar fractures for primary ORIF. The results will be analyzed by radiographic assessment of proper anatomical reduction and measurement of vertical ramus height. In addition to, clinical outcomes of pain with jaw movements and measurement of all mandibular movements range.

III. Research Question:

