What are the radiographic and clinical outcomes of using three-dimensional Delta plate for primary open reduction and internal fixation of unilateral subcondylar fractures in adult patients?

PICOTS Elements:	
Patient/Problem	Adult patients presenting with unilateral sub condylar fracture, with or without concomitant facial or mandibular fractures.
Intervention	Primary ORIF using three-dimensional delta plate
Comparator	-
Outcome	Pain, posterior facial height, anatomic reduction, mouth deviation.
Time	3 months follow up
Setting	Faculty of Dentistry-Ain Shams University

IV. Aim of the Study, Research Objectives and Clinical Relevance Aim:

The aim of the study is to assess the efficacy of the delta plate in fixation of sub condylar fractures by radiographic evaluation of anatomic reduction and vertical ramus height and clinical evaluation of pain with jaw movements and range of mandibular movements.

Outcomes:

Primary outcomes: 1-Anatomic Reduction
2-Posterior Facial Height

Secondary outcomes: 1-Pain
2-Mandibular Movements.

Clinical Relevance:

Delta plate provides functionally stable osteosynthesis. In addition to, less periosteal dissection, and easier reduction and fixation of small fragments combined with the advantages of a smaller plate size, less cost and adequate stiffness (19,23).

V. Hypothesis:

Delta plate doesn't provide an added advantage over the other Osteosynthesis methods of Sub condylar fixation.

VI. Ethical consideration

Open reduction and internal fixation of sub condylar fractures is accompanied with complications such as facial nerve injury, parotid gland fistula, permanent scar, infection, pain, edema, and difficulty in mastication following surgical procedure.

Risk of Facial injury can be decreased by choosing the appropriate incision and meticulous dissection of the tissues.

Parotid gland fistula is avoided by suturing of parotid capsule or by retroparotid-retromandibular approach whenever possible.

Permanent scar is best minimized by minimal tissue trauma, suturing in layers then the skin will be sutured by Prolene 6-0, Topical antibiotics and topical silicone gel will be prescribed.

Risk of Infection is reduced by post-operative antibiotic.

Post-operative analgesics and anti-inflammatory medications will be given to control pain and edema.

Mastication force is enhanced by physiotherapy.

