Patients are allowed to withdraw from the trial whenever they want to. In this case, they will be surgically managed by conventional plating systems. All patients will be fully informed about the procedures. The risks and benefits will be thoroughly explained to them. No surgery will be performed without written consent.

All personal information and data of the patients will be preserved, maintained and stored in a special filing system available in the department. It will not be exposed to anyone that is not included in the surgical team.

The research ethics committee, Faculty of Dentistry Ain Shams University, will review the research plan.

VII. Study Design:

Longitudinal study.

VIII. Materials and Methods:

14 patients having unilateral sub condylar fractures will undergo open reduction and internal fixation by a single 4-hole miniplate 3D Delta plate. The dimensions of this plate are 1.0 mm thick, 20mm long, 5mm wide at top and 14 mm wide at the base. At the top of the plate is an arm with two longitudinally arranged holes, two more holes form the 2 corners of the base of the plate.

Study Setting:

Department of oral and maxillofacial surgery in the Faculty of Dentistry, Ain Shams University.

Sample Size Calculation:

The sample size was estimated based on research published by Manoj et al. study (2015) regarding fracture fixation by trapezoidal 3D plate in India, by fixing alpha at 0.05 (5%) and beta at 0.05(5%), the minimal sample size is 10 patients to be included. To avoid drop out the sample was increased to 14 patients(25).

Eligibility criteria

Inclusion Criteria:

- 1-Patients at or over 18 years.
- 2-Unilateral sub condylar fractures.

Exclusion Criteria:

- 1- Bilateral sub condylar fractures
- 2-Pediatric patients.
- 3-Intracapsular fractures
- 4-Patients with Uncontrolled systematic conditions.

Justification for Exclusions:

- Most clinical and radiographic assessments of bilateral sub condylar fractures are dissimilar to that of unilateral ones.
- The management of pediatric patients is totally different from that of adults.
- Intracapsular fractures is best treated by endoscopic approach or conservatively managed
- Patients with Uncontrolled systematic conditions are unfit for surgery.

Pre-operative Assessment:

All patients will undergo radiographic assessment with Computed Tomography to assess the level of the fracture, degree and direction of displacement and shortening of ramus height by comparing the two sides.

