All patients will undergo clinical evaluation of pain, mandible deviation on opening and closing, measurement of mandibular movements.

All patients will undergo pre-operative anesthetic evaluation which includes medical and surgical history, physical examination, investigations, risk assessment, consent and pre-medication.

Surgical Procedure:

All patients will undergo open reduction and internal fixation under general anesthesia.

The Fracture will be exposed either extraorally (submandibular or retromandibular or endaural approaches). The incision will be chosen according to the level of the fracture.

Fracture will be reduced; occlusion will be re checked then it will be fixated by 2.0 mm 3D Delta mini plates and anchored by 4 screws of 7-9 mm length.

Immediate post-operative medications:

All patients will take painkillers, anti-inflammatory, antibiotics and steroids.

Follow up:

Radiographic outcomes: The following will be measured on CT:

1-The vertical ramus height will be done by comparing the two sides from the glenoid fossa to the inferior border of the ramus on CT.

2- Accuracy of anatomical reduction detected on coronal and axial sections.

Radiograph will be taken immediately post-operative.

Clinical outcomes:

1- Assessment of pain by Visual Analogue scale.

2- Mandibular movements by a ruler:

-Lateral mandibular movement by measuring the horizontal distance between upper central teeth midline to the lower central teeth midline.

-Protrusive mandibular movement by measuring the transvere distance between upper central teeth midline to the lower central teeth midline.

-Maximal mouth opening by measuring the vertical distance between upper central teeth midline to the lower central teeth midline.

Follow up notes will be taken on day three, day seven, one month and Three months postoperatively.

IX. Statistical Analysis:

Regarding the continuous date, the T dependent test will be used to assess the statistical data. Regarding the discrete data, Chi Square test will be used to assess the statistical data significance, using SPSS Software.

X. Funding of the Study:

The research study will be self-funded by the operator. No internal or external funding will be shared in this study.

XI. References:

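### The dependent t-test, the only analysis stated for ramus height (a primary outcome), does not show whether each patient's height was restored, whichever pair it is applied to

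*Protocol*

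**What the plan says.** Section IV of the Protocol lists two primary outcomes, beginning "Primary outcomes: 1-Anatomic Reduction"; the second is posterior facial height. Section II describes the radiographic part of the results as "radiographic assessment of proper anatomical reduction and measurement of vertical ramus height", so posterior facial height is read here as vertical ramus height.

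Section VIII, Follow up, gives the measurement: "The vertical ramus height will be done by comparing the two sides from the glenoid fossa to the inferior border of the ramus on CT". The timing is one CT: "Radiograph will be taken immediately post-operative". The other primary outcome is a separate item: "Accuracy of anatomical reduction detected on coronal and axial sections", with no scale attached.

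Section VIII, Pre-operative Assessment, has a matching measurement before surgery. The pre-operative CT is to assess "degree and direction of displacement and shortening of ramus height by comparing the two sides".

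Section IX has a single rule for this kind of data: "Regarding the continuous date, the T dependent test will be used to assess the statistical data". It does not say which two values form the pair, or whether a side-to-side difference keeps its sign. The Protocol gives no per-patient error measure, tolerance or margin for ramus height.

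**The concern.** The study has one arm and no comparator, so the uninjured side is the natural anatomical reference for height. Whether height has been restored is a property of each patient: a ramus 3 mm short and another 3 mm long are both unrestored, yet their signed differences average to zero. A dependent t-test addresses a mean. If it is the primary analysis of ramus height, its p-value cannot separate a series in which every patient is close to symmetric from one in which errors are large but fall in both directions. A non-significant comparison of the two sides could then be reported as restored height when it shows only that no average shift was detected in 14 patients.

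**Working it through.** **Inputs.** From the Protocol: 14 patients (sections I and VIII), a dependent t-test (section IX), a two-side CT measurement before and after surgery (section VIII). Assumed: normally distributed side differences (operated minus opposite), a two-sided 5% level, and every value in mm. The Protocol gives no SD, expected difference or tolerance for ramus height, so there is no planned figure to reproduce. The 2 mm cut-off below is illustrative only.

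**Reading A: operated versus opposite side, signed difference.** The statistic is t = mean / (SD/√14) on 13 degrees of freedom, with critical value 2.160.

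*Constructed example.* Seven patients at −5 mm and seven at +5 mm: mean 0, t = 0, p = 1.00, mean absolute error 5.0 mm. Seven at −0.1 mm and seven at +0.1 mm: mean 0, t = 0, p = 1.00, mean absolute error 0.1 mm. The mean and p-value are identical. The SD is not: √(14 × 25/13) = 5.19 mm against √(14 × 0.01/13) = 0.10 mm. Nor is the 95% CI half-width: 2.160 × 5.19/√14 = 3.00 mm against 2.160 × 0.104/√14 = 0.06 mm.

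*True mean 0.* The test is non-significant in 95% of trials at any SD. The share of patients more than 2 mm off is 2 × [1 − Φ(2/SD)].

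*True mean shortfall 1.5 mm.* The non-centrality is −1.5 × √14/SD, and the chance of non-significance is the noncentral t probability between −2.160 and +2.160.

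| SD (mm) | Mean 0: patients more than 2 mm off | Mean −1.5 mm: non-centrality | Mean −1.5 mm: chance of p > 0.05 |
|---|---|---|---|
| 1 | 5% | −5.61 | 0.07% |
| 2 | 32% | −2.81 | 26% |
| 3 | 50% | −1.87 | 59% |
| 4 | 62% | −1.40 | 74% |

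The last column does not require errors to balance. With net shortening, wider scatter alone makes the shortfall harder to detect.

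**Reading B: pre-operative versus post-operative.** The test then asks whether the side difference, or the height, changed. As a simulated illustration, take an assumed pre-operative side difference of mean −6 mm and SD 3 mm, and an independent post-operative mean of 0. The test rejects in 98 to 100% of trials whether the post-operative SD is 0.5 mm or 4 mm. At an SD of 0.5 mm practically no patient is more than 2 mm off; at 4 mm, 62% are. The result shows improvement in both cases and does not tell them apart.

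**Result.** Neither reading measures how close each patient came to symmetry.

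**The case against.** The strongest reply is that the Protocol does not fix the analysis being criticised. Section IX is one generic sentence that also covers pain and mouth opening, where only pairs over time make sense. Section VII calls the study longitudinal, and ramus shortening is measured before surgery as well. A pre- versus post-operative test fits the text, and under it any cancellation depends on whether the side difference is signed or absolute, which is not stated. This stands: side-versus-side pairing and signed coding are inferences. It does not rescue the outcome, because Reading B tests improvement.

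Several stronger readings are tempting and go beyond the documents:

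- A reader might infer that scattered reduction would look as accurate as perfect reduction. That holds for the mean and p-value only. At n = 14 the 95% CI half-width is about 0.6 mm at an SD of 1 mm and 2.3 mm at 4 mm, so a reported SD or CI would expose the scatter, and nothing in the Protocol rules out reporting one.
- A reader might infer that large errors will in fact cancel. Full cancellation needs over-lengthening about as common and as large as shortening, and the Protocol mentions only shortening. Consistent shortening would be found: a 3 mm mean shortfall with an SD of 2 mm is detected with over 99% power at n = 14.
- A reader might infer that the plan rewards imprecise surgery. That needs non-significance to be the success criterion. No section says so, and the hypothesis in section V concerns advantage over other fixation methods.

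Two further points are fair. Reduction accuracy on coronal and axial sections is a separate primary outcome, so ramus height is not the only measure of reduction; but with no scale it cannot be relied on to expose poor height restoration. And details such as coding and summary statistics are often left to an analysis plan. The point here is narrower: the test that is stated does not answer the restoration question under either pairing.

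**Conclusion.** The point holds in limited form. For ramus height the one stated analysis yields either a test of the mean side difference or a test of change from before surgery, and neither shows restoration patient by patient. Under the side-versus-side reading, non-significance is weak evidence: with an assumed 1.5 mm mean shortfall, 14 patients and normal differences, it occurs in 26% of trials at an SD of 2 mm and 74% at 4 mm, against under 1% at 1 mm.

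These are illustrations of direction and scale, not predictions, because no mm value in them comes from the Protocol. In particular, the documents do not support a statement that half the patients would be asymmetric: that figure needs an assumed SD of 3 mm, a zero mean and a 2 mm cut-off. Nor does the Protocol prescribe a signed side-to-side test; that is one plausible reading of an unspecific sentence. What remains is a worthwhile, inexpensive improvement to the analysis of a primary outcome.

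**What to change.** In section IX:

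1. Name the pair to which the dependent t-test applies for ramus height.
2. Make the primary ramus-height summary the per-patient absolute difference between operated and opposite side on the post-operative CT, in mm. Report the median, the range, and the number of patients within a tolerance that the investigators set before any CT is read, with an exact 95% CI for that proportion.
3. Keep the signed mean difference with its 95% CI, labelled as a measure of systematic shortening only.

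This takes a few sentences and uses the two heights per patient already planned, with no added imaging or patients. The downside is that natural left-right asymmetry makes the absolute difference non-zero even after ideal reduction. The Protocol gives no figure for that asymmetry, so its effect on the result cannot be sized here; the investigators should allow for it when they set the tolerance.

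### Anatomic reduction, a primary outcome, is read on coronal and axial CT only, so residual forward or backward tilt of the condylar fragment has no specified measurement

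*Protocol*

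**What the plan says.** Protocol section IV lists two primary outcomes, of which this is the first: "Primary outcomes: 1-Anatomic Reduction". The other is posterior facial height.

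The only operational description of the first outcome is item 2 of the radiographic outcomes, under Follow up in section VIII: "Accuracy of anatomical reduction detected on coronal and axial sections". The protocol mentions no sagittal section, sagittal reformat or three-dimensional reading of the CT. It also gives no angle, offset or grade by which a reduction is called accurate in any plane.

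The companion CT measurement is item 1 of the same list: "The vertical ramus height will be done by comparing the two sides from the glenoid fossa to the inferior border of the ramus on CT". On timing the protocol says: "Radiograph will be taken immediately post-operative". A CT is also taken before surgery (section VIII, Pre-operative Assessment), among other things "to assess the level of the fracture, degree and direction of displacement"; no planes are named there.

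The Background (section II) gives an angle among the indications for open surgery, "severe dislocation (> 10 degrees"), also without a plane.

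**The concern.** The orientation of a fragment needs more than two views. Coronal sections show tilt towards or away from the midline. Axial sections show rotation about the vertical axis and translation. Tipping forward or backward is rotation within the sagittal plane, and it appears as an angle in neither of the planes named.

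This differs from detail left for later documents. The protocol does specify the planes, and it names two of the three. A reader who follows it records no sagittal angle.

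What is at stake is the validity of one of two primary outcomes in a single-arm study of 14 patients, with no comparator group that would share the same measurement gap. If the outcome were summarised as a proportion of accurate reductions (the protocol does not say so), reclassifying one patient would move it by 1/14 = 7.1 percentage points.

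**Working it through.** The protocol gives no figure on this point to reproduce. Its sample size (10, raised to 14) does not depend on which planes are read. The check is geometric: how much of a sagittal tilt reaches the measurements the protocol does specify?

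**Inputs**
- Planes read: coronal and axial (section VIII, Follow up, item 2).
- Other CT measurement: ramus height, side against side (item 1).
- Fragment length L: not in the documents. Assumed 20 to 30 mm.
- Tilt t: assumed purely sagittal, at 10, 20 and 30 degrees.

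**Formulas**, for a rigid fragment pivoting at the fracture line:
- Angle seen on the coronal view = 0 degrees.
- Loss of vertical length = L × (1 − cos t).
- Front-to-back shift of the condylar head = L × sin t.

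All of the vertical loss is allowed to pass into the measured ramus height, which is generous to that outcome as a backstop.

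**Results**

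| Tilt | Coronal angle | Height loss, L = 20 / 25 / 30 mm | Head shift, L = 20 / 25 / 30 mm |
|---|---|---|---|
| 10° | 0° | 0.30 / 0.38 / 0.46 mm | 3.47 / 4.34 / 5.21 mm |
| 20° | 0° | 1.21 / 1.51 / 1.81 mm | 6.84 / 8.55 / 10.26 mm |
| 30° | 0° | 2.68 / 3.35 / 4.02 mm | 10.0 / 12.5 / 15.0 mm |

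Worked line: with L = 25 mm and t = 20°, the loss is 25 × (1 − 0.9397) = 1.51 mm and the shift is 25 × 0.3420 = 8.55 mm.

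**Mixed tilt.** With 5 degrees in the coronal and 20 degrees in the sagittal plane, the true angle is arctan √(tan² 5° + tan² 20°) = arctan √(0.00765 + 0.13247) = arctan 0.3743 = 20.5 degrees. The coronal view reads 5.

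**Reading the table.** Height falls with the cosine of the tilt and so barely responds at 10 degrees: half a millimetre or less. It begins to respond at 20 to 30 degrees, with about 1 to 4 mm. The front-to-back shift responds much more strongly and lies in a direction that axial slices display, but item 2 specifies no offset to be recorded.

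**The case against.** The best reply is that the malposition is not hidden. Axial is one of the two named planes, and a rigid fragment that tilts must show a front-to-back displacement: at the head if the head leaves the fossa, at the fracture line if it stays seated. A reader who sees an offset of several millimetres is not obliged to call the reduction accurate. This stands. What the plan leaves unmeasured is the sagittal angle, not every trace of the malposition.

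Four stronger readings are tempting, and the documents do not support them.

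- *A sagittally malreduced fragment counts as reduced.* The protocol gives no scoring rule for any plane, so nothing makes a coronal angle of 0 degrees a success. It can be scored so; it need not be.
- *The primary outcome is biased towards success.* A missed residual tilt would flatter the post-operative reading. But a fracture displaced mainly in this plane would also show little correction in the planes read, which would understate benefit if values before and after surgery are compared. Section IX plans a dependent t-test for continuous data, so that effect is possible too. No net direction is established.
- *The pre-operative reading is wider than the post-operative one.* The pre-operative passage names no planes. That is silence, not evidence that three planes are read.
- *A tilt above 10 degrees fails the protocol's own standard.* That angle is a background indication for surgery with no plane attached. It is not a criterion for residual angulation and serves here only as a reference point.

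It is also fair to say that the calculation describes one hypothetical fragment. The documents do not say how often predominantly sagittal tilt occurs.

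**Conclusion.** The point holds in limited form. As written, the first primary outcome includes no measurement of forward or backward angulation. Such angulation can be noticed only indirectly, through an axial offset that the protocol does not ask to be recorded, or through ramus height, which is a poor backstop at 10 degrees and a partial one at 20 to 30. A sagittally malreduced fragment can therefore be scored as accurately reduced.

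The millimetre figures rest on an assumed 20 to 30 mm rigid fragment and on purely sagittal tilt, neither of which comes from the documents. The frequency of the problem and its net effect on the trial result cannot be derived from them. Severity is low to moderate: a real gap in how a primary outcome is measured, cheap to close, but not shown to change the conclusion.

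**What to change.** Replace item 2 of the radiographic outcomes (section VIII, Follow up) with:

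> Accuracy of anatomical reduction, measured on coronal, sagittal and axial reformats of the same CT, with residual angulation recorded in both the coronal and sagittal planes and fore-aft offset recorded, each compared with the uninjured side, on the pre-operative and immediate post-operative CT.

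The uninjured side is available as a reference because only unilateral fractures are eligible. Naming both scans also settles which planes are read before surgery, so that values before and after can be compared like with like.

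The cost is one sentence and a few minutes of extra reading per scan. Sagittal reformats come from CT data already being acquired, so there is no extra imaging, visit or patient, and the sample size is unaffected. The change concerns outcome measurement only. It does not by itself supply a rule for calling a reduction accurate, which would still have to be stated in advance.

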Research Code

Radiographic and Clinical Evaluation of Three-Dimensional Delta Plate in Internal Fixation of Mandibular Sub-condylar Fractures.

(Longitudinal Study)

Research Protocol

Submitted to the Department of Oral and Maxillofacial Surgery

Faculty of Dentistry, Ain Shams University.

**In partial fulfillment of the requirements of Masters' degree in Oral
and Maxillofacial Surgery.**

By:

[name]

**B.D.S. Faculty of Dentistry Ain Shams University
2019**

Email: [contact]

Under the Supervision of:

[name].[name]

Professor of Oral and Maxillofacial Surgery
Faculty of Dentistry
Ain Shams University

[name] [name]

Lecturer of Oral and Maxillofacial Surgery
Faculty of Dentistry
Ain Shams University

[name] [name]

Fellow of Oral and Maxillofacial Surgery
Ahmed Maher Teaching Hospital

Year of protocol registration

2023

Table of Contents

Topic	Page
I. Abstract	4
II. Background	5
III. Research Question	8
IV. Aims (Objectives)	9
V. Hypothesis	10
VI. Ethical Considerations	11
VII. Study design	13
VIII. Materials and Methods	14
• Study setting	15
• Sample Size	16
• Study Procedures	17
IX. Statistical Analysis	18
X. Funding of the Study	19
XI. References	20
XII. Arabic summary	23

I. Abstract:

Management of Sub-condylar fractures has been debatable for years, some surgeons advocate closed management if the situation permits, to avoid the complications associated with open reduction and internal fixation (ORIF). Nowadays, there are meticulous approaches and novel osteosynthesis systems that facilitate its open management but many of these systems need more research work to evaluate its efficacy.

In this study we intend to examine the efficacy of 3D delta plates from the radiographic and clinical point of view. This Single arm study will include 14 cases of trauma having mandibular sub condylar fractures, in which open reduction and internal fixation are indicated. After selecting patients according to the inclusion criteria, all patients will undergo open reduction and rigid fixation. Fracture will be stabilized using 4 hole, 2.0 mm 3-D Delta titanium plates using pre-auricular or retromandibular incision.

Postoperative clinical examination will be carried out on day three, day seven, one month and after three months. Postoperative radiographic examination will be performed immediately postoperative by CT scan.

II. Background:

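### The first primary outcome, accuracy of anatomical reduction, has no stated scale or threshold and no stated link to the pre-operative CT, so the protocol does not determine which planned test applies

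*Protocol*

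**What the plan says.** Section IV lists "Primary outcomes: 1-Anatomic Reduction", with posterior facial height as the second primary outcome. Under Follow up in section VIII, the radiographic outcomes are introduced by "Radiographic outcomes: The following will be measured on CT". For reduction, the definition that follows is "Accuracy of anatomical reduction detected on coronal and axial sections". The timing is given by "Radiograph will be taken immediately post-operative".

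The Pre-operative Assessment in section VIII has every patient undergo CT "to assess the level of the fracture, degree and direction of displacement and shortening of ramus height by comparing the two sides".

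Section IX assigns the dependent t-test to continuous data. For discrete data it states that "Chi Square test will be used to assess the statistical data significance". It does not allocate individual outcomes to the two tests.

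The Abstract states "This Single arm study will include 14 cases of trauma", and the comparator entry in the section III table is a dash.

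**The concern.** A primary outcome should be fixed well enough that two people reading the same scan would record the same kind of value. Here the protocol fixes the imaging planes and the time, but not what is recorded. It could be an angle, a distance, an ordinal grade or a judgement that the fracture is reduced.

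Two things are at stake. First, if the scale and any definition of success are still open when the post-operative scans are available, they can be settled with the results in view, and a single-arm study has no comparison group to restrain that choice. Second, the choice of scale decides whether either planned test can be used. The pre-operative CT supplies a natural baseline in its "degree and direction of displacement and shortening of ramus height by comparing the two sides", but the outcome definition does not say that the post-operative scan is read on the same measure.

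**Working it through.** **1. How each outcome is specified (section VIII)**

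| Outcome | What is recorded | Unit, scale or landmarks |
|---|---|---|
| Anatomic reduction (primary) | Accuracy, on coronal and axial CT | None stated |
| Posterior facial height, as ramus height (primary) | Height, compared between sides | Anatomical end points stated |
| Pain (secondary) | Score | Visual analogue scale |
| Mandibular movements (secondary) | Ruler distances | Reference points stated |

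The outcome listed first is the least specified of the four.

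**2. What each possible scale means for the planned tests**

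- *Continuous, on both CTs:* the data are paired and the planned dependent t-test applies.
- *Continuous, on the post-operative CT only:* there is no second value to pair, so the dependent t-test has no input. A mean with a confidence interval is still possible.
- *Categorical, on the post-operative CT only:* there is one group at one time. Chi-square has no second group, and no reference proportion is given for a one-sample version.
- *Categorical, on both CTs:* the two readings come from the same patients, so an ordinary chi-square test of independence does not fit.

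The protocol does not say which of these is meant.

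**3. Size under a post-operative yes/no reading**

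The inputs are n = 14 (Abstract, section VIII) and, if losses bring the number down to the stated minimum, n = 10 (Sample Size Calculation). When all n succeed, the exact (Clopper-Pearson) two-sided 95% lower limit is 0.025^(1/n).

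- 14 of 14: 0.025^(1/14) = 0.768, so 76.8% to 100%.
- 12 of 14 (from beta quantiles): 57.2% to 98.2%.
- 10 of 10: 0.025^(1/10) = 0.692, so 69.2% to 100%.

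A one-sample chi-square needs a reference proportion p0. With 14 of 14 successes the statistic is 14(1 − p0)/p0 on 1 degree of freedom. The p0 values below are assumptions, because the protocol gives none.

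| p0 (assumed) | Expected failures | Statistic | p |
|---|---|---|---|
| 70% | 4.2 | 6.00 | 0.014 |
| 80% | 2.8 | 3.50 | 0.061 |
| 90% | 1.4 | 1.56 | 0.21 |
| 95% | 0.7 | 0.74 | 0.39 |

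The same perfect result is significant or not depending on a figure the protocol does not state. Every expected failure count is below 5, so the chi-square approximation is also doubtful.

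**4. Size under a continuous reading**

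For a mean residual or a mean paired change, the 95% half-width in units of that quantity's SD is t(0.975, n − 1)/√n. With n = 14 this is 2.160/3.742 = 0.58 SD. The SD is not given, so this cannot be turned into degrees or millimetres, nor compared directly with the binomial intervals.

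**5. The sample size does not settle the scale**

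The minimum of 10 is stated with alpha and beta both 0.05, but without an endpoint, effect or SD. It cannot be re-derived, and it gives no hint of how reduction was meant to be measured.

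**The case against.** The strongest defence is that the protocol is silent rather than wrong. A reader might infer that reduction will be a yes/no judgement made after the scans are seen. Nothing in the text says so: the heading speaks of measuring on CT, and accuracy suggests a quantity at least as readily as a category. The intervals and chi-square results in step 3 therefore describe one possible reading, not the plan as written.

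A reader might also infer that no planned test could analyse this outcome, or that the baseline comparison has been discarded. Neither is supported. If displacement is quantified on both CTs, the planned dependent t-test applies, and a one-sample chi-square would be possible if a reference proportion were set. The protocol does not say that the two scans will be read differently; it fails to say that they will be read alike.

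Nor does the gap leave the radiographic question wholly unanswered. Posterior facial height is a separate primary outcome, with landmarks, a side-to-side comparison and a pre-operative counterpart.

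Finally, matching outcomes to tests is often left to an SAP, and one may exist that is not shown. That covers the choice of test. It does not cover what is measured as a primary outcome, which belongs in the protocol. All these limits on the point stand, and the missing definition remains.

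**Conclusion.** The point holds in limited form and should be corrected. The first primary outcome has no scale, no threshold and no stated link to the displacement recorded before surgery, so the protocol does not settle which of its two tests applies. In one case, a categorical reading of the single post-operative CT with no reference proportion, neither test has anything to compare, and even 14 of 14 successes would not exclude a true rate as low as 76.8%.

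That figure assumes a yes/no reading and no losses among the 14 patients. The conclusion that the outcome is undefined rests on the protocol text alone and needs no assumption.

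**What to change.** In section VIII, define anatomic reduction as residual angulation in degrees and residual displacement in millimetres. State which coronal and axial sections and which reference lines are used, and whether values are signed or absolute. Measure both the same way on the pre-operative and the immediate post-operative CT.

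In section IX, make the post-operative residual, with its mean and 95% confidence interval, the main measure of accuracy. Give the paired change from the pre-operative CT, by dependent t-test, as support. The residual should lead because open reduction is done to reduce displacement, so a test against zero change says little about how accurate the reduction was.

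If a category of reduced versus not reduced is also wanted, fix its cut-off before any post-operative CT is read, and report the proportion with an exact binomial interval instead of a chi-square test.

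The cost is protocol wording and a few extra minutes of measurement per CT. Both scans are already planned, so no additional imaging or patients are needed.
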